5.5.3 Rescue Medications & Supportive Care

Participants should receive appropriate supportive care measures as deemed necessary by the treating investigator. Suggested supportive care measures for the management of AEs with potential immunologic etiology are outlined along with the dose modification guidelines in Section 5.2.2, (Table 3). Where appropriate, these guidelines include the use of oral or IV treatment with corticosteroids, as well as additional anti-inflammatory agents if symptoms do not improve with administration of corticosteroids. Note that several courses of steroid tapering may be necessary as symptoms may worsen when the steroid dose is decreased. For each disorder, attempts should be made to rule out other causes such as metastatic disease or bacterial or viral infection, which might require additional supportive care. The treatment guidelines are intended to be applied when the Investigator determines the events to be related to pembrolizumab.

Note: If after the evaluation of the event, it is determined not to be related to pembrolizumab, the Investigator does not need to follow the treatment guidance. Refer to (Table 3) in Section 5.2.2 for guidelines regarding dose modification and supportive care.

It may be necessary to perform conditional procedures such as bronchoscopy, endoscopy, or skin photography as part of evaluation of the event.

5.5.4 Local Therapy and Treatment Beyond Disease Progression

Local therapy for brain metastases:

Local therapy in the form of craniotomy, LITT, or SRS can be performed on symptomatic brain lesions prior to assessment for study eligibility, provided all neurologic side effects from the procedure have resolved and all other eligibility criteria are met. At any time point throughout the study, local therapy (surgery, LITT, or SRS) will be administered to a lesion that becomes clinically concerning if deemed necessary by the investigators. This can be followed by continuation on pembrolizumab and lenvatinib, provided that the patient is otherwise benefiting from therapy and has stable disease or disease shrinkage in other lesions by RECIST criteria. Approval from the study PI or co-PIs is required to continue treating the patient on pembrolizumab and lenvatinib. Craniotomy and LITT are considered major procedures and require temporary holding of lenvatinib as detailed in Section 5.2.2.15. SRS is considered a minor procedure and does not require holding of lenvatinib. Further details for holding lenvatinib are detailed in Section 5.2.2.15.

A brain metastasis that has been treated locally will not be considered evaluable for response and will not be included when calculating the sum of largest dimensions. If the treated lesion constitutes >25% of the target lesions (for example, if one of three target lesions is treated locally), this will be considered progressive disease. If >75% of the baseline lesions are not treated with local therapy and evaluable by imaging, the patient will be considered evaluable, and response for the primary endpoint analysis will be assessed based on the remaining lesions. Additional response evaluation will be performed which will consider those patients who require local therapy while on study as having PD at the time of local therapy.

Local therapy for extra-cerebral metastases:

Local surgery or radiation therapy (if indicated for palliative measures only after discussion with the study PI or co-PIs) may be permitted and the patient can continue to receive pembrolizumab and lenvatinib provided there is otherwise evidence of clinical benefit from treatment (i.e. stable disease or response in measurable lesions). The criteria applied for assessing response is detailed in Section 7.1.2.9.

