RECIST 1.1 limits the number of lesions measured to 5 in total, with 2 per organ. For our purposes, even if there are multiple measurable lesions in the brain, the sum of diameters of up to a maximum of 5 of the largest lesions will be considered for response assessment.

Modified response criteria for brain metastases

Complete Response (CR): Disappearance of all target lesions.

Partial Response (PR): At least a 30% decrease in the sum of diameters of target lesions, taking as reference the baseline sum diameters.

Progressive Disease (PD): At least a 20% increase in the sum of diameters of target lesions, taking as reference the smallest sum recorded since the treatment started or the appearance of one or more new lesions (new lesions must be greater than slice thickness).

Stable Disease (SD): Neither sufficient shrinkage to qualify for PR nor sufficient increase to qualify for PD, taking as reference the smallest sum diameters since the treatment started. Please refer to RECIST v1.1 for additional details regarding response criteria.

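### The on-study local-therapy rule for the primary response assigns no outcome to one of four treated targets, can assign two outcomes if non-target lesions count, and drops the treated lesion

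*Combined protocol and SAP*

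**What the plan says.** Section 5.5.4 provides that local therapy on study "will be administered to a lesion that becomes clinically concerning if deemed necessary by the investigators". A lesion so treated is no longer evaluable and "will not be included when calculating the sum of largest dimensions". Two branches then settle the patient's status:

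- PD branch: "If the treated lesion constitutes >25% of the target lesions (for example, if one of three target lesions is treated locally", the case is progressive disease.
- Evaluable branch: "If >75% of the baseline lesions are not treated with local therapy and evaluable by imaging, the patient will be considered evaluable". For a patient who passes this test, the section then says how the endpoint is read: "response for the primary endpoint analysis will be assessed based on the remaining lesions".

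A supplementary analysis follows: "Additional response evaluation will be performed which will consider those patients who require local therapy while on study as having PD", dated at the local therapy.

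Section 7.1.2.9.4 sets the measurement rules. For brain targets, "the sum of diameters of up to a maximum of 5 of the largest lesions will be considered for response assessment". Partial response (PR) is a decrease of at least 30%, "taking as reference the baseline sum diameters". The section also recognises non-measurable lesions at baseline. For patients who need local therapy it refers the reader to Section 7.1.2.9, but neither that section nor its subsections contain a rule for them. Section 8.2 rejects the null at 4 or more responses in 27 (melanoma) and 7 or more in 29 (renal cell carcinoma, RCC).

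**The concern.** A rule that feeds the primary endpoint should give each patient exactly one classification. This one has two strict inequalities on two denominators (target lesions and baseline lesions). The second denominator is not defined, and no order of precedence is given. Some patients may therefore fall under neither branch and others under both, which leaves the classification to judgement in an open-label, single-arm trial.

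The evaluable branch raises a separate question. The lesion removed from the response is the one that became clinically concerning after treatment began, so the set of lesions measured depends on how they behaved. The cohort decisions rest on small counts, so the classification of a single patient can matter.

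**Working it through.** **Inputs.** The 25% and 75% thresholds and their denominators come from 5.5.4. The maximum of five targets and the PR threshold of a 30% decrease come from 7.1.2.9.4. The decision rules come from 8.2.

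**The plan's own example.** One of three targets treated is 1/3 = 33.3%, which exceeds 25%, so PD. This reproduces.

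**General form.** Let one target be treated, with T targets and N untreated, evaluable non-targets that count as baseline lesions.

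- PD if 1/T > 1/4, that is, T of 3 or fewer.
- Evaluable if (T + N − 1)/(T + N) > 3/4, that is, T + N of 5 or more.
- Neither: T = 4 and N = 0.
- Both: T of 3 or fewer and T + N of 5 or more.

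| Targets | Non-targets counted | Treated / targets | Untreated / baseline | Outcome |
|---|---|---|---|---|
| 1 | 0 | 100% | 0% | PD |
| 2 | 0 | 50% | 50% | PD |
| 3 | 0 | 33.3% | 66.7% | PD |
| 4 | 0 | 25.0% | 75.0% | none |
| 5 | 0 | 20% | 80% | evaluable |
| 3 | 1 | 33.3% | 75.0% | PD |
| 3 | 2 | 33.3% | 80% | PD and evaluable |
| 2 | 3 | 50% | 80% | PD and evaluable |
| 1 | 4 | 100% | 80% | PD and evaluable |
| 4 | 1 | 25.0% | 80% | evaluable |

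If baseline lesions means targets only, just the rows with no non-targets apply: the gap at four targets remains and the conflict disappears. If evaluable non-targets count, the conflict appears, and the gap is confined to patients with four targets and no other such lesion.

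**Dropping the treated lesion.** Assumed diameters: baseline 20 + 10 + 10 + 10 + 10 = 60 mm; follow-up 28 + 7 + 7 + 7 + 7 = 56 mm. The 28 mm lesion is then treated (one of five, so evaluable).

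- All five lesions: (56 − 60)/60 = −6.7%, stable disease.
- Treated lesion removed from both sums: (28 − 40)/40 = −30%, which meets the PR threshold.

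So resetting the baseline does not remove the effect.

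**Sensitivity of the decisions.** The probability of rejecting is the sum, over stage 1 counts that continue, of P(X1 = x) × P(X2 ≥ r − x), both binomial.

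- Melanoma (stop at 0 of 13; reject at 4 of 27): type I error 0.0416 at 5%, power 0.8011 at 20%.
- RCC (stop at 2 or fewer of 18; reject at 7 of 29): 0.0497 at 12%, power 0.8014 at 30%. The 12% null is an assumption, taken from the historical rate cited in 8.2.

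Both fit the stated 0.05 and 80%. Now suppose, purely as an assumption, that the rule adds false responders in 1, 2, 3 or 5 percentage points of patients. Type I error becomes:

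- melanoma: 0.072, 0.111, 0.159, 0.271
- RCC: 0.071, 0.097, 0.129, 0.206

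This shows how steeply the designs react. It does not estimate the effect in this trial.

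**The case against.** The best defence is that the rule is prespecified, that it gives PD whenever one of one, two or three targets is treated and no non-targets count, and that a stricter evaluation is already planned. Continuing on drug also requires stable or shrinking disease in the other lesions. This limits the practical reach of the dropped lesion. It does not alter which version is primary, and it does not close the gap.

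The conflict between branches is open to a fair challenge. Up to five of the largest measurable lesions become targets, so non-targets beside three or fewer targets would mostly be non-measurable, and the evaluable branch asks for lesions that can be evaluated on imaging. If such lesions do not count, there is no conflict. That objection stands as a limit: the conflict belongs to one reading of an undefined term. The term still needs a definition, because a small lesion can be visible without being measurable, and the text does not say whether visible is enough.

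A reader might infer three stronger things that the documents do not support.

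- *Patients caught in the gap are replaced, which raises the response rate.* The Trial Schema note (2.2) and Section 5.7 tie unevaluability to not reaching the first scan. A scanned patient who stays on treatment does not meet that. Section 8.3 calls all analyses intent to treat, under which a patient without a category would more naturally stay in the denominator as a non-responder.
- *A patient can be a partial responder with no lesion shrinking.* Take one 30 mm and four 5 mm targets (50 mm), treat the large one, and keep the baseline: 50 to 20 mm is −60%. But reading response on the remaining lesions more naturally removes the treated lesion from both sums, giving 20 to 20 mm, no change. The wording should say so, but this example is not what the plan most plainly means.
- *The error rate is materially inflated.* No frequency of on-study local therapy is given, so no size can be claimed.

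**Conclusion.** The rule is incomplete as written. One treated of four targets has no outcome when those are the only baseline lesions or when the term means targets. On the reading that includes evaluable non-targets, the rule is also contradictory for three or fewer targets with at least five lesions in all. In the evaluable branch the primary response omits the treated lesion, which can turn stable disease into PR even with a matched baseline; the diameters used to show this are assumed. The effect on either cohort's decision is unquantified. The point merits correction because the rule governs the primary endpoint and nothing elsewhere repairs it, not because a bias of known size has been shown.

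**What to change.** For endpoint classification only, leaving untouched when local therapy is given and whether study treatment continues:

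1. Use target lesions as the denominator in both branches.
2. Make PD apply at 25% or more, so that the branches are complementary. One treated of one to four targets is then PD and one of five is evaluable.
3. State that the treated lesion is removed from both the baseline and the follow-up sums.
4. State how a treated non-target is classified, since a target-only denominator does not register it.
5. Put the rule in Section 7.1.2.9, where 7.1.2.9.4 already points.

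Steps 1 to 3 remove the gap and the conflict but still drop the lesion in the one-of-five case. Preferably, therefore, make the planned supplementary evaluation the primary classification: any on-study local therapy counts as PD at the time of that therapy, so responses confirmed earlier stand. The remaining-lesions version becomes the sensitivity analysis. This also covers non-targets.

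The cost is wording, since both evaluations are already planned. The downside is a possibly slightly lower primary response rate.

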4.2.3 Rationale for Endpoints

4.2.3.1 Efficacy Endpoints

Primary endpoint:

Best brain metastasis response rate (BMRR), defined as PR and CR per modified RECIST 1.1.

Secondary endpoints:

Best overall objective response rate, defined as PR and CR per RECIST 1.1.

PFS, defined as the time from start of study drug administration to the date of the first documentation of disease progression or death from any cause, whichever occurs first.

OS, defined as the time from start of study drug administration to date of death from any cause.

Duration of brain metastasis response, defined as the time from response to the time of the first documentation of intracranial disease progression.

Safety and rate of adverse events, particularly neurologic adverse effects, which include worsening of edema and development of radiation necrosis.

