7.1.2.9.8 Progression-Free Survival (PFS)

PFS is defined as the time from initiation of study drug until the first documented, confirmed progression of clinically evaluable brain metastases based on mRECIST criteria, systemic disease based on RECIST criteria, or death. If there is progression of disease that is then confirmed on a follow up scan at least 4 weeks later, the initial date of documented progression should be used in the PFS analysis.

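### Local therapy to a brain metastasis outside the >25%-of-targets rule ends neither intracranial response duration nor PFS, so both can be lengthened in a subset of unknown size

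*Combined protocol and SAP*

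**What the plan says.** Section 5.5.4 permits local treatment of brain lesions throughout the study: "At any time point throughout the study, local therapy (surgery, LITT, or SRS) will be administered to a lesion that becomes clinically concerning". Study drugs may then continue with approval, provided that the patient is otherwise benefiting and other lesions are stable or shrinking. For assessment, "A brain metastasis that has been treated locally will not be considered evaluable for response and will not be included when calculating the sum".

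A threshold follows. Where local treatment takes in more than a quarter of the targets, with one in three given as the example, "this will be considered progressive disease". On the other side, "If >75% of the baseline lesions are not treated with local therapy and evaluable by imaging, the patient will be considered evaluable", and the primary endpoint is then assessed on the remaining lesions. The section closes with a further analysis: "Additional response evaluation will be performed which will consider those patients who require local therapy while on study as having PD", dated at the time of the local therapy.

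Section 4.2.3.1 has duration of brain metastasis response "defined as the time from response to the time of the first documentation of intracranial disease progression". Section 7.1.2.9.8 ends PFS at the "first documented, confirmed progression of clinically evaluable brain metastases based on mRECIST criteria", at confirmed systemic progression by RECIST, or at death. Section 8.3 analyses both by Kaplan-Meier and censors patients without an event at the last clinical evaluation. None of these three sections mentions local therapy.

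**The concern.** Secondary objective 3 in Section 3.2 asks how long the drugs hold the brain response. If a lesion that is escaping control is irradiated or resected before a scan documents progression, and it is then left out of the sum, the clock keeps running. Part of the reported duration is then owed to the procedure. The same applies to PFS.

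The timing of scans makes this plausible. After week 12, imaging is 12 weeks apart (Section 7.1.2.9.2), so a lesion can be treated on clinical concern between scans.

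The patients exposed to the gap are ones the trial wants. Section 4.2.1 criticises another study for not addressing patients with more than 4 brain metastases and says that this trial targets that population. Section 7.1.2.9.4 allows up to 5 target lesions, so a patient with more than 5 necessarily has lesions that are not targets.

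The plan already provides an analysis with local therapy as PD, but Section 8.3 does not carry it over to the endpoints that measure time.

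**Working it through.** **Plan's own figures.** The only sized endpoint is intracranial response. An exact two-stage binomial calculation reproduces the designs in Section 8.2:
- Melanoma (stop at 0 of 13, reject at 4 or more of 27): alpha 0.0416 at a 5% rate, power 0.801 at 20%.
- RCC (stop at 2 or fewer of 18, reject at 7 or more of 29): alpha 0.0497 at 12%, power 0.801 at 30%. The plan does not label 12% as the null; it is the reference rate quoted there.

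PFS and response duration have no stated sizing to reproduce.

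**Step 1: where the PD rule applies.** Shares are taken by number of lesions, as the protocol's example of one in three implies, and baseline lesions are read as target lesions.

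| Targets | Treated | Share treated | PD (>25%)? | Evaluable (>75% untreated)? |
|---|---|---|---|---|
| 1 | 1 | 100% | yes | – |
| 2 | 1 | 50% | yes | – |
| 3 | 1 | 33% | yes | – |
| 4 | 1 | 25% | no | no: 75% is not above 75% |
| 5 | 1 | 20% | no | yes (80%) |
| 4 | 2 | 50% | yes | – |
| 5 | 2 | 40% | yes | – |

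Two treated targets are PD for any count from 2 to 5. Treatment of a target escapes the rule only for one of 4 or one of 5. Treatment of a baseline non-target lesion also escapes it, because the rule counts targets only. One of four is neither PD nor clearly evaluable.

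**Step 2: does PD under the rule reach the time-to-event endpoints?** Section 5.5.4 declares PD because of a procedure. Section 7.1.2.9.8 asks for confirmed progression by mRECIST, and the mRECIST definition of PD in Section 7.1.2.9.4 (growth of the sum, or new lesions) has no limb for local therapy. How such PD is confirmed, and on what date, is not said. Section 7.1.2.9.4 sends the reader to Section 7.1.2.9 for patients needing local therapy, but no rule is there. The rule is in 5.5.4.

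**Step 3: direction.** For each patient, the earlier of progression and local therapy cannot be later than progression alone. Leaving local therapy out therefore lengthens the observed time or leaves it unchanged.

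**Step 4: size, as an illustration.** Assume constant, independent hazards. Let h be the hazard of all events for the endpoint, with local therapy included, and q the share of those events that are uncounted local therapies. The counted hazard is (1-q)h, the median is ln 2 divided by the hazard, and so the median is multiplied by 1/(1-q).

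| q (assumed) | Factor | Median if the full one is 6 months (assumed) |
|---|---|---|
| 5% | 1.05 | 6.3 |
| 10% | 1.11 | 6.7 |
| 20% | 1.25 | 7.5 |
| 30% | 1.43 | 8.6 |

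For PFS, q is the share of all PFS events, including systemic progression and death. If half of PFS events were intracranial (an assumption) and 20% of those went uncounted, q = 0.5 x 0.20 = 0.10 and the factor is 1.11, not 1.25.

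**Step 5: numbers of responders.** At the design rates, 0.20 x 27 = 5.4 melanoma and 0.30 x 29 = 8.7 RCC responders are expected. One uncounted case is 1/5.4 = 19% or 1/8.7 = 11% of the responders in its cohort.

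**The case against.** A reader might infer that local therapy is never an event for these endpoints. The documents do not support that. Treating one of 1 to 3 targets, or two or more of 4 or 5, is PD under Section 5.5.4, and a new lesion larger than slice thickness is PD under Section 7.1.2.9.4. Some procedures will also follow PD already recorded. Section 2.1 describes SRS or surgery for symptomatic lesions in patients treated beyond intracranial progression, and Section 5.5.2 describes radiation to a lesion that is already progressing.

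A reader might also infer that every local therapy marks a failure of the drugs, so that both durations are certainly inflated and only the version counting local therapy should be believed. That does not follow either. The trigger is clinical concern and investigator judgement, and Sections 4.2.1 and 4.2.3.1 expect oedema and radiation necrosis. Counting every procedure as failure can understate drug control. This stands, and it is why the two versions belong side by side.

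Third, the additional analysis dates PD at the local therapy, which is what a duration endpoint needs, so it may have been meant to carry over. That is possible, but the text calls it a response evaluation and Section 8.3 is silent.

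Finally, both endpoints are descriptive secondary ones with no test. That limits the consequence but does not remove the gap.

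**Conclusion.** The point holds in a limited form. When the treated lesion is one of 4 or 5 targets, or a baseline non-target lesion, it leaves the assessment without ending intracranial response duration or PFS, and no planned analysis of either endpoint shows the effect. This is a possible upward bias in a subset of unknown size, not a demonstrated one.

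The factors of 1.11 at q = 10% and 1.25 at q = 20% rest on constant, independent hazards and on assumed values of q. The same uncounted procedures weigh less in PFS, where systemic progression and death also count. With about 5 and 9 expected responders, one or two such cases could move a median response duration.

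Separately, it is unclear whether and when PD under the >25% rule counts for PFS, and the case of exactly 25% is undefined. The Simon decision rules and the sample size are unaffected.

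**What to change.** In Section 8.3, add a sensitivity analysis of intracranial response duration and of PFS in which any on-study local therapy to a brain metastasis is an event on its date. Report it beside the mRECIST-based version, with the number of patients whose result differs.

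Three clarifications belong with it:
- State that PD under the >25% rule counts for both endpoints on the date of local therapy, without needing confirmation by imaging.
- Settle how one treated target of four is classified, since neither threshold in Section 5.5.4 covers it, and say whether baseline lesions there means target lesions.
- Correct the cross-reference in Section 7.1.2.9.4 so that it points to Section 5.5.4.

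The cost is one more analysis run. The dates are already needed for the additional response evaluation in Section 5.5.4, and neither treatment nor sample size changes. The drawback is that the added version may understate drug control where the procedure was for oedema or radiation necrosis. Recording the reason for each procedure would help readers to judge that.
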